12.2 Period of Observation

For the purposes of this study, the period of observation for collection of adverse events extends from the date of signature of the informed consent until 100 days after the last day of study treatment except for adverse events related to study drug, which must be reported during follow-up period until resolution or initiation of further anti-tumor therapy.

If an Investigator detects a serious adverse event in a study subject after the end of the period of observation, and considers the event possibly related to prior study treatment, he or she should contact the Sponsor to determine how the adverse event should be documented and reported.

At each visit/assessment AEs will be assessed from information collected from the source documents and information transcribed into the CRF.

12.3 Documentation and Reporting of Adverse Events by Investigator

All adverse events that occur during the observation period set in this protocol must be documented on the pages provided in the case report form in accordance with the instructions for the completion of adverse event reports in clinical studies. These instructions are provided in the case report form itself.

The following approach will be taken for documentation:

- All adverse events (whether serious or non-serious, or considered as an alert term) must be documented on the “Adverse Event” page of the case report form.
- If the adverse event is serious, the investigator must complete, in addition to the “Adverse Event” page in the case report form, a “Serious Adverse Event/Expedited Report from a Clinical Trial” form at the time the serious adverse event is detected.

This form must be faxed to the IFCT’s Pharmacovigilance department.

Every attempt should be made to describe the adverse event in terms of a diagnosis. If a clear diagnosis has been made, individual signs and symptoms will not be recorded unless they represent atypical or extreme manifestations of the diagnosis, in which case they should be reported as separate events. If a clear diagnosis cannot be established, each sign and symptom must be recorded individually.

All patients who have adverse events, whether considered associated with the use of the investigational products or not, must be monitored to determine the outcome. The clinical course of the adverse event will be followed up according to accepted standards of medical practice, even after the end of the period of observation, until a satisfactory explanation is found or the investigator considers it medically justifiable to terminate follow-up. All questions on the completion and supply of adverse event report forms and any further forms issued to the investigator at a later date to clarify unresolved issues should be addressed to the IFCT.

12.4 Immediate Reporting by Investigators to IFCT

Serious adverse events and adverse events that fulfil a reason for expedited reporting to Pharmacovigilance must be documented on a “Serious Adverse Event/Expedited Report from a Clinical Trial” form in accordance with the “Instructions for completing the ‘Serious Adverse Event/Expedited Report from a Clinical Trial’ form”. This form must be completed and supplied to the Sponsor within 24 hours or at the latest on the following working day. The “Serious Adverse Event/Expedited Report from a Clinical Trial” form and the instructions are provided in the investigator’s study file.

The initial report must be as complete as possible, including details of the current illness and (serious) adverse event, and an assessment of the causal relationship between the event and the investigational product(s). The report will be completed in the electronic case report form. In case of unavailability of the CRF, a paper report will be sent by e-mail to [contact]. An acknowledgment of receipt will be sent to the site.

Information not available at the time of the initial report (e.g., an end date for the adverse event or laboratory values received after the report) must be documented on a follow-up “Serious Adverse Event/Expedited Report from a Clinical Trial” form.

The “Instructions for completing the ‘Serious Adverse Event/Expedited Report from a Clinical Trial’ form” give more detailed guidance on the reporting of serious adverse events, adverse events that comply with alert terms, and adverse events initially reported as non-serious that become serious. In the latter situation, when a non-serious event becomes serious, details must be forwarded immediately to the Sponsor on a “Serious Adverse Event/Expedited Report from a Clinical Trial” form.

12.5 Reporting of pregnancy

The investigator is required to report to the sponsor any pregnancy where the embryo/fetus could have been exposed to durvalumab. This means pregnancies occurring in female participants, female partners of male participants, or females exposed through direct contact with the agent during their pregnancy (for example, environmental exposure involving direct contact with the agent). Pregnancies occurring up to 90 days after the completion of durvalumab must also be reported.

12.6 Overdose

An overdose is defined as a subject receiving a dose of durvalumab in excess of that specified in the Investigator’s Brochure, unless otherwise specified in this protocol.

Any overdose of a study subject with durvalumab, with or without associated AEs/SAEs, is required to be reported within 24 hours of knowledge of the event to IFCT. Patient Safety or designee using the designated Safety e-mailbox (see Section 10.3.2 for contact information). If the overdose results in an AE, the AE must also be recorded as an AE (see Section 10.3). Overdose does not automatically make an AE serious, but if the consequences of the overdose are serious, for example death or hospitalization, the event is serious and must be recorded and reported as an SAE (see Section 10.1.2 and Section 10.3.2). There is currently no specific treatment in the event of an overdose of durvalumab.

The investigator will use clinical judgment to treat any overdose.

13 PROTOCOL TREATMENT DISCONTINUATION AND THERAPY AFTER STOPPING

13.1 Criteria for Discontinuing Protocol Treatment

Patients may stop protocol treatment in the following instances:

- Intercurrent illness which would, in the judgement of the investigator, affect assessments of clinical status to a significant degree, and require discontinuation of protocol therapy.
- Unacceptable toxicity as defined in Section 7.5 and Appendix II.
- Disease relapse or new primary invasive malignancy as defined in Section 10.
- Request by the patient.
- Pregnancy or intent to become pregnant
- Initiation of alternative anticancer therapy including another investigational agent.
- Completion of therapy as outlined in Section 7. Efforts should be made to maintain the investigations schedule and continue follow-up, even if patients discontinue protocol treatment prematurely and/or no longer attend the participating institution.

13.2 Withdrawal of study

The Reasons for withdrawal of study are:

- - Withdrawal of consent by the patient,
- - Relapse or 2nd cancer,
- - Death,

Patients have the right to withdraw their consent and ask to leave the study at any time and for whatever reason (they are not required to explain). This should not affect their right to a subsequent management. The investigator must do everything to avoid withdrawal of consent.

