- 2 TSH may be completed within 7 days prior to visit.
- 3 Must be contrast enhanced CT scan, low dose surveillance CT is not acceptable. To ensure comparability, the baseline scans and subsequent scans to assess response must be performed using identical techniques (i.e. scans performed immediately following bolus contrast administration using a standard volume of contrast, the identical contrast agent, and preferably the same scanner).
- 4 When relapse is first documented at any site, complete restaging is required to identify all sites of relapse.

9.3 Evaluation after disease relapse or new invasive primary malignancy (during or after protocol treatment)

Should a patient relapse or develop a new invasive primary malignancy (as defined in Section 10) during the trial, details should be entered in the EDC disease event form and patient follow-up will be altered. All study patients must have a visit 4 weeks, 6 months and one year after surgery.

Treatments received by the patient after relapse and for new primary malignancies will be left to the discretion of the patient and his/her physician, but all treatments will be recorded in the EDC case report forms. All sites of NSCLC relapse or new primary malignancies will be recorded on the case report forms.

Follow up visit according to the centre practice.

Investigations		Timing
Physical Exam including:	
 • subsequent anti-cancer therapy • physical examination including pulse, blood pressure • performance status 	Every follow up visit.
Hematology	
 • CBC including hemoglobin, differential, platelet count 	Only at 4 week post surgery. Thereafter as clinically indicated only or to follow durvalumab related AEs until resolution to grade 0-1.
Biochemistry	
 • AST (SGOT) and ALT (SGPT) • alkaline phosphatase • bilirubin • creatinine 	Only at 4 week post surgery. Thereafter as clinically indicated only or to follow durvalumab related AEs until resolution to grade 0-1.
	
 • TSH¹ 	At 4 week and then as clinically indicated, or to follow durvalumab related AEs until resolution to grade 0-1. ²
	
 • INR/APTT 	As clinically indicated.
Radiology	
 • CT scan chest and upper abdomen • other imaging as clinically indicated if suspicion of relapse or new primary invasive malignancy 	According to current guidelines.

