Other Investigations	
 • ECG • urinalysis • pregnancy test if applicable 	As clinically indicated.
	
 • Lung function tests: FEV1, FVC, TLCO and SaO2 at room atmosphere 	Repeat if pulmonary symptoms/suspicion of pneumonitis.
Adverse Events	Patients must be evaluated for durvalumab related adverse events at each visit, including late events.	

1 If TSH is abnormal, both T3 and T4 should be measured (both are recommended but at least one of T3 or T4 is mandatory if TSH is abnormal).

2 TSH may be completed within 7 days prior to scheduled visit.

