11.1.4 Disease-free Survival

Disease-free survival shall be measured from the day of inclusion until any of the following events: day of documented equivocal or definite relapse (local, regional or distant), diagnosis of a new primary invasive cancer (except squamous cell carcinoma and basal cell carcinoma of skin and any in situ cancer, completely excised and presumed cured), or death from any cause.

NOTE: Patients with Equivocal Changes should be re-imaged at the next planned time or earlier if clinically indicated. If relapse/new primary malignancy is confirmed the date of event is taken from the date that equivocal changes were first described.

Relapse will be categorized as local/regional or distant.

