11.1.7 Overall Survival

Overall survival is defined as the time from inclusion to the time of death (from any cause) or to the date the patient was last known to be alive.

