13.5 Follow-up Off Protocol Treatment

All patients will be seen at 4 weeks, 6 months and one year after surgery. Thereafter, patients without evidence of disease relapse or new primary malignancy will be followed as per schedule outlined in Section 8.2. Patients that have relapsed disease or new primary malignancy as per definitions in Section 10 will continue to be followed until death as outlined in Section 8.3.

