15.4 Study Endpoints and Analysis

The primary endpoint will be performed on all eligible patients based on patient percentage surgical resection R0 after a maximum of 3 cycles of chemotherapy. It will be presented associated with confidence interval of 95%.

DFS is a secondary endpoint, defined as the time from the date of inclusion to the date of first documented disease relapse or the occurrence of a new invasive primary malignancy or death from any cause. Patients who are alive and disease/new invasive primary malignancy-free at the time of each analysis will be censored at their last disease assessment date.

OS is a secondary endpoint, defined as the time from the inclusion to the date of death of any cause, or censored at their last known alive date. All analysis on DFS will be carried out for the OS endpoint.

The analysis of secondary endpoints will be performed on patient eligible.

Although PD-L1 expression as measured by immunohistochemistry is hypothesized to be a potential predictive marker, this is as yet not validated in either the adjuvant or palliative settings. Further, the cut-off defining PD-L1 positivity has not been validated. This trial will also explore the utility of PD-L1 as a predictive biomarker as well as the optimal cut-off for positivity.

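### Section 13.2 withdraws patients from the study at relapse or second cancer, while 9.3 and 13.5 keep following them; applied literally, 13.2 would bias overall survival upward

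*Protocol*

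**What the plan says.** Section 13.2 gives three reasons for withdrawal from the study: withdrawal of consent, "Relapse or 2nd cancer", and death. It does not say which data collection ends at withdrawal.

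Other sections of the protocol treat the same patients differently:

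- **13.5:** patients with relapse or a new primary "will continue to be followed until death as outlined in Section 8.3".
- **9.3**, the section on evaluation after relapse or a new primary: "All study patients must have a visit 4 weeks, 6 months and one year after surgery". Later anti-cancer treatments are to be recorded, and "Patients must be evaluated for durvalumab related adverse events at each visit, including late events".
- **13.1:** relapse or a new primary is already listed as a reason to stop protocol treatment, with the instruction that "Efforts should be made to maintain the investigations schedule and continue follow-up, even if patients discontinue protocol treatment prematurely".

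OS is a secondary endpoint. It runs from inclusion to death from any cause (11.1.7), and patients not known to have died are "or censored at their last known alive date" (15.4).

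**The concern.** Consent withdrawal and death, the other two items in 13.2, both end a patient's participation. Read with them, the relapse item tells a site that participation ends at relapse. Sections 9.3 and 13.5 say that it does not.

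If a site follows 13.2 and stops recording vital status, the last date known alive is roughly the relapse date. The patients censored this way are those most likely to die next. The censoring is therefore informative, and the Kaplan-Meier OS estimate is too high. If every relapsed patient were lost, the curve would count only deaths without relapse. Part of the late safety evaluation that 9.3 requires would also be lost.

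This has to be settled in the protocol, because an analysis plan cannot recover follow-up that was never collected.

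**Working it through.** **1. Can 13.2 mean only the end of treatment?** No. Section 13.1 already covers stopping treatment at relapse, and treatment lasts one month from the first infusion (8.6, 13.3), so most relapses will come after it has ended. No section says that patients withdrawn under 13.2 remain in survival follow-up.

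**2. Does the protocol lead the reader to the intended rule?** Not reliably. Section 13.5 refers to sections 8.2 and 8.3. In the current numbering these are Premedication and Patient Monitoring during infusion; the schedules meant are 9.2 and 9.3.

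**3. Direction and size of the bias.** The protocol states no OS figure to reproduce and no relapse or post-relapse death rates. All inputs below are assumptions, with constant hazards:

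- 1-year disease-free survival (DFS): 65%, 75% or 85%
- death without relapse: 5% per year, so μ = −ln(0.95) = 0.0513
- relapse hazard: λ = −ln(DFS) − μ
- median survival after relapse: 0.5, 1 or 2 years, so ν = ln 2 / median
- share f of relapsed patients lost at relapse: 25%, 50% or 100%

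Formulas:

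- alive without relapse: D(t) = exp[−(λ+μ)t]
- alive after relapse: P(t) = λ/(ν−λ−μ) × {exp[−(λ+μ)t] − exp(−νt)}
- true OS(t) = D(t) + P(t)
- Kaplan-Meier limit at 1 year = exp{−∫₀¹ [μD + (1−f)νP] / [D + (1−f)P] dt}

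Mid case (DFS 75%, median 1 year): λ+μ = 0.2877, λ = 0.2364, ν = 0.6931.

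- P(1) = 0.2364/0.4055 × (0.75 − 0.50) = 0.146, so true OS = 0.750 + 0.146 = 89.6%.
- With f = 100% the limit is exp(−μ) = 95.0%. With f = 50% it is 92.1%, and with f = 25% it is 90.8%.

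Full grid at 1 year:

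| DFS | Median after relapse (years) | True OS | Overstatement in points at f = 25 / 50 / 100% |
|---|---|---|---|
| 65% | 0.5 | 80.9% | 2.9 / 6.2 / 14.1 |
| 65% | 1 | 86.7% | 1.7 / 3.6 / 8.3 |
| 65% | 2 | 90.7% | 0.9 / 1.9 / 4.3 |
| 75% | 0.5 | 85.8% | 2.1 / 4.3 / 9.2 |
| 75% | 1 | 89.6% | 1.2 / 2.5 / 5.4 |
| 75% | 2 | 92.2% | 0.6 / 1.3 / 2.8 |
| 85% | 0.5 | 90.5% | 1.1 / 2.2 / 4.6 |
| 85% | 1 | 92.3% | 0.6 / 1.3 / 2.7 |
| 85% | 2 | 93.6% | 0.3 / 0.7 / 1.4 |

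**4. Patients involved.** Of the planned 77 (15.2), relapses within one year number 77 × λ/(λ+μ) × (1 − DFS). That is 7.9 at DFS 85%, 15.8 at 75% and 23.7 at 65%. Deaths after relapse within that year are the relapses minus 77 × P(1), which gives 1.3 to 11.5 over the grid.

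**5. Other assumptions.** With 12-month relapse risk 15–30%, death without relapse 5% and median survival after relapse 6–18 months, the 12-month overstatement is 0.6–2.8 points at 25% loss, 1.2–5.9 at 50% and 2.6–13.4 at 100%. The bias is upward in every scenario.

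**6. With follow-up kept (f = 0).** The Kaplan-Meier limit equals true OS, so the bias is zero.

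**The case against.** The strongest reply is that one list item stands against several explicit instructions to keep following, and that 13.2 never says data collection stops. Relapse may simply end the 9.2 schedule, which covers the period before relapse, and start the 9.3 schedule. That may well be what was intended, but the protocol does not say so.

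The size can also be challenged, and this largely stands. Every rate and every share lost is assumed, and the 14.1-point limit needs all sites to ignore 9.3 and 13.5 for all relapsed patients. The model also censors at the instant of relapse, whereas routine CT after surgery is six-monthly (9.2). If relapses are detected only at a first postoperative scan, assumed to fall 7.5 months after inclusion, the mid-case overstatement drops from 1.2 / 2.5 / 5.4 to 0.5 / 1.0 / 2.2 points at 25 / 50 / 100% loss, and the worst corner drops from 14.1 to 4.9. Earlier detection through symptoms would raise these figures. The direction does not change.

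Two further points stand:

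- The safety loss is narrower than 9.3 alone suggests. Section 12.2 ends reporting of drug-related events at resolution or the start of further anti-tumour therapy, which many relapsed patients would begin anyway. Section 12.3 requires events to be followed to outcome even after the observation period.
- DFS is mostly, but not wholly, protected. A qualifying relapse or new primary is itself the DFS event. But 13.2 says second cancer without restriction, while 11.1.4 excludes squamous and basal cell skin cancers and in situ cancers that are completely excised and presumed cured. A patient withdrawn for one of these would be censored for DFS without an event.

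Finally, the section references are out of step elsewhere in the protocol too, so that fault is not specific to 13.5.

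**Conclusion.** The contradiction is real, and 13.2 is wrong as written: a site that follows it literally breaks 9.3 and 13.5 and biases OS upward. The direction is certain once vital status is lost at relapse. The size is illustrative only. On the assumed rates it is about 0.3 to 6.2 points of 1-year OS if a quarter to a half of relapsed patients are lost, and up to 14.1 points in the extreme; it is smaller if relapse is detected late. There is no bias if all sites follow 9.3 and 13.5.

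The R0 primary endpoint, the sample size and the two-stage decision rule are unaffected, and the effect on DFS is limited to the excluded second cancers. The point should be corrected, but it does not threaten the main conclusion of the trial.

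**What to change.** - Delete "Relapse or 2nd cancer" from the list in 13.2.
- State in 13.2 that relapse or second cancer moves the patient to the 9.3 schedule, and that vital status is collected until death or end of study unless consent is withdrawn.
- For second cancers that 11.1.4 does not count as DFS events, state that DFS follow-up continues as well.
- In 13.5, change the references from 8.2 and 8.3 to 9.2 and 9.3.

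The cost is a short protocol correction and a note to sites. The survival follow-up adds no data beyond what 9.3 and 13.5 already require.

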13.3 Duration of Protocol Treatment

Treatment will continue for one month from the date of the first infusion.

13.4 Therapy After Protocol Treatment

Anti-cancer therapy after surgery is at the discretion of the investigator. Adjuvant platinum based chemotherapy and adjuvant radiation are allowed, according the current guidelines.

Subsequent anti-cancer therapy will be collected on the CRFs.

13.5 Follow-up Off Protocol Treatment

All patients will be seen at 4 weeks, 6 months and one year after surgery. Thereafter, patients without evidence of disease relapse or new primary malignancy will be followed as per schedule outlined in Section 8.2. Patients that have relapsed disease or new primary malignancy as per definitions in Section 10 will continue to be followed until death as outlined in Section 8.3.

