4 These exams should have been analysed before surgery by primary physician and surgeon to confirm the operability.

9.2 Evaluation after protocol treatment but prior to disease relapse/new invasive primary malignancy

The following investigations are to be performed for the period after discontinuation of durvalumab and surgery.

All patients must be seen at 4 weeks after surgery. Follow up visits then occur at 6 months and one year and then according to current guidelines.

	Investigations	Timing
Physical Exam including:	
 physical examination including blood pressure performance status Concomitant medication Adverse events 	Every follow up visit
Hematology	
 CBC including hemoglobin, differential, platelet count 	Only at 4 weeks after surgery. Thereafter as clinically indicated only or to follow durvalumab related AEs until resolution to grade 0-1.
Biochemistry	
 AST (SGOT) and ALT (SGPT) alkaline phosphatase Total bilirubin (if total bilirubin is $\geq 2x$ ULN (and no evidence of Gilbert's syndrome) then fractionate into direct and indirect bilirubin Gamma glutamyltransferase albumin creatinine Urea CRP Magnesium Potassium Bicarbonate sodium Calcium Chloride Total protein 	Only at 4 weeks after surgery. Thereafter as clinically indicated only or to follow durvalumab related AEs until resolution to grade 0-1.
	
 TSH¹ 	At 4 week after surgery and then as clinically indicated, or to follow durvalumab related AEs until resolution to grade 0-1. ²
	
 INR/APTT 	As clinically indicated.
Radiology ³	
 CT scan chest and upper abdomen³ other imaging as clinically indicated if suspicion of relapse or new primary invasive malignancy⁴ 	6 monthly for one year and then according to current guidelines.
Other Investigations	
 ECG 	4 weeks after surgery then as clinically indicated
	
 urinalysis pregnancy test if applicable 	As clinically indicated.
	
 lung function tests: FEV1, FVC, TLCO and SaO2 on room air 	Only if pulmonary symptoms or suspicion of pneumonitis (see Section 7.5 for full recommendations).

- 1 If TSH is abnormal, both T3 and T4 should be measured (both are recommended but at least one of T3 or T4 is mandatory if TSH is abnormal).

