15.2 Sample Size, Power

The maximum sample size (N) is calculated based on α , β , and the expected effect size, using a test for single binomial proportion for a two-stage design with a 1:1 randomization and O'Brien-Fleming (OF) stopping rules, allowing for early stopping for futility after Stage I. The software East 6.0 was used.

The rate of complete resection equal to or lower than 85% (P0) is considered as unacceptable after immune treatment. On the other hand, we can conclude to a good rate of complete resection if it is 95% (P1). The computation is based on the following assumption, considering the probability of compliance: P0 =85%; P1 = 95%; statistical power of 0.90; type I error rate (one-sided) of 0.05.

The null hypothesis that the rate of complete resection is P0 = 85% will be tested against a one-sided alternative. In the first stage, 39 patients will be accrued. If there are 34 or fewer responses in these 39 patients, the study will be stopped for futility. Otherwise, 38 additional patients will be accrued for a total of 77. The null hypothesis will be rejected if 71 or more responses are observed in 77 patients. To take into account 5% of ineligible patients, 81 patients will be included.

Duration of accrual: 18 months and 1 year follow-up.

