16.4.1 Study schedule

The protocol should begin at 2nd quarter of 2016. The trial recruitment period is expected to be 32 months, follow-up is one year. The trial should be ended by mid-June 2020.

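### Sections 9.2, 13.2, 13.5, 15.2 and 16.4.1 conflict on how long and for whom survival is followed, so censoring of overall survival can depend on relapse

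*Protocol*

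**What the plan says.** Follow-up after surgery is described in several places in the protocol.

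- **13.5, relapsed or new-primary patients:** "Patients that have relapsed disease or new primary malignancy as per definitions in Section 10 will continue to be followed until death".
- **13.5, relapse-free patients:** after the one-year visit, "patients without evidence of disease relapse or new primary malignancy will be followed as per schedule outlined in Section 8.2". Section 8.2 is now the premedication section; the schedule meant is evidently 9.2.
- **9.2:** "Follow up visits then occur at 6 months and one year and then according to current guidelines". No interval or end date is given after one year.
- **9.3, after relapse:** the visits at 4 weeks, 6 months and one year remain required; otherwise "Follow up visit according to the centre practice".
- **13.2:** relapse or a second cancer is listed, with death and withdrawn consent, as a reason for withdrawal of study.
- **Section 4 scheme and Appendix I:** follow-up is shown at 4 weeks, 6 months and one year after surgery, and nothing later.
- **15.2:** "Duration of accrual: 18 months and 1 year follow-up".
- **16.4.1:** "The trial recruitment period is expected to be 32 months, follow-up is one year. The trial should be ended by mid-June 2020".

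OS runs from inclusion to death from any cause, "or censored at their last known alive date" (15.4; 11.1.7 agrees). Neither section names a common cut-off.

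**The concern.** Kaplan-Meier estimation requires that a patient censored at a given time has the same prognosis as those still at risk. Relapse strongly predicts death. If relapse decides whether a patient stays under observation, that requirement fails.

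The sections allow this in both directions. Longer follow-up after relapse (13.5) leaves the later risk set enriched with patients who have relapsed. Withdrawal at relapse (13.2) removes those patients before they die. A uniform one-year stop (15.2, 16.4.1) does neither, but ends the curve there. Sites could apply any of these in good faith.

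The accrual conflict adds to the uncertainty. It does not itself create relapse-dependent censoring, but it changes how much follow-up exists beyond one year.

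DFS is much less exposed, because relapse or a new primary is already the DFS event.

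**Working it through.** **Plan figure.** The protocol states no OS rate, event count, power or time horizon, so there is no OS figure to reproduce.

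**Inputs from the protocol.** Surgery is no later than 6 weeks after the first infusion (10.1), taken as 1.5 months after inclusion. The one-year visit then falls at 1.5 + 12 = 13.5 months. If the trial closes one year after the last surgery, the longest possible follow-up is 18 + 13.5 = 31.5 months with 18-month accrual, or 32 + 13.5 = 45.5 months with 32-month accrual.

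**Assumptions, not in the protocol.** Constant hazards; relapse risk r at 12 months of 10, 20 or 30%; median survival m after relapse of 12 or 24 months; death without relapse at 0.2% per month.

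**Formulas.** Relapse hazard λ = −ln(1 − r)/12; post-relapse death hazard μ = ln 2/m; death without relapse ν = 0.002; κ = λ + ν.

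- *True OS:* S(t) = e^(−κt) + [λ/(κ − μ)]·[e^(−μt) − e^(−κt)].
- *Reading 1: relapse-free patients stop at 13.5 months, relapsed patients continue.* After 13.5 months only relapsed patients are at risk, so the estimate at 24 months tends to S(13.5)·e^(−10.5μ).
- *Reading 2: relapse-free patients contacted every 6 months after one year (assumed interval), relapsed patients followed to the cut-off.* Simulated, 400,000 patients per scenario.
- *Reading 3: relapsed patients withdrawn and censored at relapse.* Only death without relapse is seen, so the estimate tends to e^(−24ν) = e^(−0.048) = 0.953.
- *Reading 4: everyone stops at 13.5 months.* No 24-month estimate.

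**Worked case, r = 20%, m = 12 months.** λ = 0.018595, μ = 0.057762, κ = 0.020595, so S(13.5) = 0.907 and S(24) = 0.790. Reading 1 gives 0.907 × e^(−0.6065) = 0.907 × 0.545 = 0.494, which is 0.790 − 0.494 = 0.296 too low. Reading 3 gives 0.953 − 0.790 = 0.163 too high.

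**24-month OS and bias in percentage points:**

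| r, m | True OS | Reading 1 | Reading 2, accrual 18 / 32 months | Reading 3 |
|---|---|---|---|---|
| 10%, 12 | 0.870 | −36 | −2.3 / −0.9 | +8 |
| 10%, 24 | 0.904 | −20 | −1.7 / −0.6 | +5 |
| 20%, 12 | 0.790 | −30 | −3.0 / −1.1 | +16 |
| 20%, 24 | 0.857 | −16 | −2.0 / −0.8 | +10 |
| 30%, 12 | 0.715 | −24 | −3.1 / −1.3 | +24 |
| 30%, 24 | 0.812 | −13 | −2.0 / −0.8 | +14 |

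The simulation gives the same ranges for readings 1 and 3 as the formulas. At 36 months, which only 32-month accrual reaches, reading 2 is about 2 to 3 points too low.

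**At 12 months,** readings 1, 2 and 4 are unbiased. Reading 3 is already too high: 0.98 against a true 0.89 to 0.96.

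**After the fix.** With vital status collected equally for all to one cut-off, the simulated 24-month estimate equals true OS in every scenario.

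**The case against.** A reader might infer that only relapsed patients are followed past one year, so that OS is biased downward by tens of points. The documents do not support that as the expected result. Section 13.5 sends relapse-free patients to the 9.2 schedule, which continues under current guidelines. With regular contact the bias is 1 to 3 points, below the sampling error of a trial this size: at OS 0.79, √(0.79 × 0.21/77) = 0.046, or 4.6 points. The 13 to 36 points belong to the extreme reading. Nor is the direction settled, since section 13.2 points the other way.

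Section 13.2 may also be loose wording. Section 9.3 requires visits after relapse, and 13.1 asks that follow-up continue after treatment stops. That makes reading 3 less likely, but 13.2 still says the opposite of 13.5.

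Follow-up to death is ordinarily understood to end at trial closure, and 16.4.1 gives an expected end of mid-June 2020. The cut-off date and the length of the plotted curve can be left to an analysis plan. No section promises a 24-month OS estimate, and OS has no hypothesis or comparator here. All of this stands.

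What remains is a matter of data collection. An analysis plan can set a cut-off, but it cannot recover vital status that was never collected or undo withdrawal at relapse. Guideline follow-up after one year carries no stated duty to report vital status to the trial.

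**Conclusion.** The point holds as an inconsistency with a possible bias of unsettled direction. The five sections do not agree on how long and for whom survival is followed, and the OS censoring rule passes that disagreement into the estimate. At 24 months the result could be about 13 to 36 points too low, 1 to 3 points too low, 5 to 24 points too high, or not estimable, according to the section applied.

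These sizes rest on the assumed relapse and death rates, constant hazards, and the assumed 6-monthly contact in reading 2. The logical point, that censoring can depend on relapse, needs none of them.

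The consequence is limited to OS beyond about one year, or earlier if relapsed patients are withdrawn. OS is a secondary endpoint. The R0 endpoint is settled at surgery, so it and the sample size of 77 evaluable (81 included) patients are untouched. The correction should be made, but it does not threaten the trial's main conclusion.

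**What to change.** 1. Reconcile 9.2, 13.2, 13.5, 15.2 and 16.4.1 into one follow-up rule, and correct the references in 13.5 to sections 8.2 and 8.3.
2. State in 13.2 that relapse or a second cancer does not end survival follow-up.
3. Collect vital status for every included patient, relapsed or not, up to one common cut-off date, for example one year after the last patient's surgery. Censor OS at that date or at true loss to follow-up. If this is not feasible, truncate OS for all patients at one year after surgery.
4. State one accrual duration in 15.2 and 16.4.1.

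The cost is protocol wording and one vital-status query per patient at the cut-off, with no added visits or procedures. The truncation alternative gives up OS information beyond one year.
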